## **BACKGROUND**

Social anxiety is a prevalent anxiety disorder that manifests as extreme fear of negative evaluation by others in social settings and avoidance of social interaction (Kashdan & Herbert, 2001). Social anxiety involves a pervasive experience of heightened anxiety and behavioral avoidance in social and performance situations with an overestimation of negative evaluation by others (i.e., negative social cues are salient or neutral cues are misinterpreted as negative) and/or a failure to appropriately process positive social feedback (i.e., positive social cues are less salient). Social anxiety disorder is the most common anxiety disorder in the United States, with a lifetime prevalence rate of 7-13% (Bogels et al., 2010; Furmark, 2002).

Unlike other anxiety disorders, social anxiety is particularly common among adolescents (5-15% lifetime prevalence; Heimberg et al., 2000; Lewinsohn et al., 1993), with average onset occurring during early to mid-adolescence (Rapee & Spence, 2004; Schneider et al., 1992). Given that the majority of social anxiety begins before the age of 18 years (Otto et al., 2001), adolescence and young adulthood is a particularly important developmental period for exploring innovative methods for intervening and preventing the negative sequelae that can result from social anxiety disorder. Social anxiety disorder in adolescence can be associated with substance abuse (Clark et al., 1996), externalizing and antisocial behavior (Davidson et al., 1993), and high rates of suicidal ideation (Francis et al., 1992), making it a critical mental health issue.

One innovative method of addressing anxiety-related conditions is the growing field of animal-assisted interventions (AAIs). AAIs incorporate animals for the purpose of meeting therapeutic goals (Jegatheesan et al., 2014). Initial evidence has demonstrated that AAIs can be effective in treating a number of mental health symptoms (Nimer & Lundhal., 2007; Souter & Miller, 2007), including anxiety (Barker & Dawson, 1998; Barker et al., 2015). Furthermore, there is evidence that contact with animals in a variety of therapeutic and non-therapeutic settings can buffer cardiovascular responses to stress (Allen et al., 1991, 2002), and social stress in particular (Polheber & Matchock, 2013).

AAIs are a particularly promising treatment option for adolescents, as engaging adolescents in traditional therapeutic treatments such as psychotherapy can be challenging, due in part, to perceived stigma (Oetzel & Scherer, 2003). The nonjudgmental nature of animals has been frequently cited as a critical component of effectiveness in various types of AAIs, providing motivation and courage to engage in a difficult activity (e.g., reading; Friesen, 2009), promoting positive social engagement (Grandin et al., 2015), providing acceptance and attention during therapy (Parish-Plass, 2008), and supporting decreased stress response (Allen et al., 2002). Furthermore, human-animal interaction has been associated with a number of positive developmental outcomes in adolescence, particularly regarding social relationships and empathic behaviors (Mueller, 2014). Given the importance of the adolescent period for social development, AAI may also be a pathway to positive outcomes in addition to promoting symptom reduction for adolescents with varying levels of social anxiety.

However, despite the promise of AAIs, several key barriers limit their use as a treatment option for social anxiety. First, the field of human-animal interaction more broadly lacks research documenting the specific mechanisms of action by which AAIs produce therapeutic outcomes. There have been repeated calls for research that addresses the specific processes driving different types of AAIs (e.g., Hoagwood et al., 2016; Kazdin, 2015). Isolating the effects of specific activities within AAIs is critical in understanding how to best design interventions for maximal therapeutic impact. For example, despite the fact that anxiety reduction has received a significant amount of attention in the AAI literature, it is still unclear exactly *how* interacting with animals can promote anxiety reduction.

Our primary goal is to test the mechanism by which AAIs reduce anxiety (**Aim 1**). There are at least two possible hypotheses for the processes underlying anxiety reduction in AAIs. First, social support is broadly associated with beneficial psychological and physiological functioning (for review, see Uchino, Cacioppo, & Kiecolt-Glaser, 1996). In particular, social support can buffer the effects of laboratory based stressors (Heinrichs et al., 2003). According to Social Baseline Theory (Coan & Sbarra, 2015), humans are inherently social, and evaluate challenges based on their ability to meet goals. Part of this implicit calculation includes social relationships (e.g. friends, family, colleagues) that might be helpful in meeting goals. One possibility is that when a person interacts with an animal, a relationship is formed that becomes part of the person's representation of social resources. For instance, being around a friendly dog might decrease the possibility of being surprised by another human or animal, thus reducing risk and decreasing anxiety. Therefore, the first mechanism we will test is whether social interaction with an animal buffers anxiety in the presence of a social stressor.

Another possible mechanism for anxiety reduction is physical touch. Since the famous "wire mother" studies by Harlow & Zimmerman (1959), researchers have explored the effects of physical touch, though the topic remains relatively understudied (Field, 2010). Most touch research has focused on interpersonal touch between two humans (for review, see Gallace & Spence, 2010). Research has found touch can reduce the experience of pain (Mancini et al., 2014) and influence heart rate, even in young children (Fairhurst et al., 2014). In a hospital setting, touch can reduce anxiety and blood pressure (though these findings are moderated by gender; Whitcher & Fisher, 1979). Less research has looked at how touching animals can influence anxiety, but initial evidence suggests that physical contact with a dog may be an important component of the interaction (Vormbrock & Grossberg, 1988; though this research has significant methodological weaknesses). Increased physical touching of a dog is correlated with less of a cortisol response in children with attachment disorders during laboratory induced stressors (Beetz et al., 2012). The second mechanism we will test is whether physically touching an animal buffers anxiety above and beyond social support alone. Initial research has suggested that contact with an animal was associated with lower anxiety than social contact with a human friend (Polheber & Matchock, 2013), suggesting that physical touch may be an important additive factor for reducing anxiety.

In addition, there is a lack of research on whether AAIs benefit adolescents with social anxiety in particular. Although existing literature supports the scientific premise that animal contact can buffer anxiety, this effect has primarily been tested in healthy adults (Allen et al., 2002; Polheber & Matchock, 2013), children with attachment disorders (Beetz et al., 2012; Wedl et al., 2015), and children with autism spectrum disorder (O'Haire et al., 2015). Our secondary goal is to specifically test the effectiveness of AAIs for adolescents with varying levels of social anxiety (**Aim 2**).

Finally, AAI research has suffered from methodological weaknesses, relying heavily on self-report measurement, non-random assignment to experimental/treatment conditions, and small sample sizes (Herzog, 2015). Although self-report measures are useful, it is critical to use multiple outcome measures for a more robust understanding of how a therapeutic strategy as complex and nuanced as AAI can be effective. The proposed study will overcome these methodological barriers by using a combination of measurement approaches, randomized experimental design, and an adequately powered study design.

Overall, the **objective** of this study is to address several key theoretical and methodological barriers in AAI research by assessing the effectiveness of different types of contact with a dog in reducing social anxiety using a robust study design with multiple measurement approaches.

## APPROACH

The primary aim of this study is to test the mechanisms by which interacting with animals reduce anxiety (**Aim 1**). The second aim is to determine if the anxiolytic effect of contact with a dog is moderated by the level of pre-existing social anxiety in adolescents (**Aim 2**). To achieve these aims, we will complete a randomized, controlled laboratory experiment that uses a powerful and well-validated social evaluative stressor, the Trier Social Stress Task for Children (TSST-C; Buske-Kirschbaum et al., 1997). To understand and measure the anxiety reducing effects of interacting with animals, we will collect three levels of outcome data: a) self-reported experience (anxiety), b) autonomic physiology (heart rate), and c) cognitive performance (error rates on mental math task).

## **Participants and Procedure**

*Eligibility Criteria:* To test the mechanism by which interacting with a dog can impact social anxiety, we will enroll 75 adolescents on a continuum of social anxiety. Given the importance of mid to late adolescence as a developmentally important period for social anxiety disorder, we will recruit adolescents ages 13-17. Individuals who are interested in participating will be screened for social anxiety using the Social Anxiety Scale for Adolescents (SAS-A; La Greca & Lopez, 1998). Parental consent and youth assent will be obtained for the screening process. The SAS-A was designed for use in adolescence and has been validated extensively across many samples and in multiple languages (e.g., Garcia-Lopez et al., 2011; La Greca & Lopez, 1998). The SAS-A contains 18 items that include three domains of social anxiety: fear of negative evaluation from peers, social avoidance and distress in new situations, and generalized social avoidance. Based on existing research suggesting the assessment of social anxiety on a continuum as compared to categories (McNeil, 2001), we will use stratified random sampling to select a balanced sample of individuals who range across low, mid, and high social anxiety (as defined by scores of  $>50$  [high anxiety] and  $<36$  [low anxiety] as recommended by La Greca, 1999). Exclusion criteria will include fear of or allergy to dogs. In total, we will enroll 75 participants (25 randomized to three conditions).

*Recruitment:* Participants will be recruited from the Massachusetts area by leveraging Tufts University resources (e.g., Tufts University School of Medicine, existing contacts through the Tufts Paws for People group, local clinics and educational programs). Parents/guardians of potential participants will be contacted via email or phone. Flyers and email announcements will be sent to relevant listserves.

*Screening procedure:* Interested participants will be provided with a link to an online screening survey. The online screener will be used to assess pre-existing level of social anxiety to inform stratified randomization, as well as exclusion criteria. Eligible participants will then be contacted with information regarding the full experimental study.

*Experimental Procedure:* During the experimental session, participants will first be informed about the study, and if consent is given by the individual (and legal parent or guardian) they will be enrolled as a participant. To test the mechanism by which interacting with dogs can reduce anxiety, participants will be randomly assigned to one of three conditions that vary the nature of the interaction: 1) interaction with a stuffed toy dog (control condition); 2) social interaction (no physical contact) with a real dog; and 3) social + physical interaction with a real dog. We will not include a physical interaction only condition because it would be impractical to block the possibility for social interaction while allowing physical interaction. A stuffed toy dog will be used as an active control condition to control for the novelty of an animal-related stimulus.

Participants in all three conditions will listen to a therapy animal handler speak for several minutes about his or her dog and view a photo of the dog, in order to further control for the novelty effects of an animal stimulus and to provide a baseline rest period (20 minutes). During this rest period, participants will also complete the first self-report anxiety questionnaire and be fitted to the wearable heart rate device.

In the control condition (1), participants will listen to the verbal presentation but there will be no animal present. Instead, there will be a stuffed toy dog (Beetz et al., 2012) and a person (to mirror the therapy dog handler). In both animal interaction conditions, one therapy dog and his or her handler will accompany the participant during all phases of the TSST-C. In the social interaction condition (2), participants will be told that the dog will be present, and they can socially interact with it at any point during the experiment (i.e., talking, social referencing), but they will not be permitted to touch the dog. In the social + physical interaction condition (3), participants will be told that the dog will be next to them and that they will be encouraged to interact socially and touch the dog during the experiment. Animal handlers are will be trained to provide consistently minimal verbal contact, to reduce the confounding effects of handler variability and distraction from the TSST-C tasks. All dog/handler teams will be approved through the Pet Partners animal therapy organization, and per the Pet Partners guidelines, all dogs will be on a 6' leash. To simulate a typical AAI environment, the handler will remain in proximity to the dog to monitor his/her behavior, but will not block the participant or interfere with the TSST-C tasks in any way.

The primary task all participants will complete is the Trier Social Stress Task for Children (TSST-C), which involves six distinct phases: baseline, anticipation, preparation, speech, mental math, and recovery (Buske-Kirschbaum et al., 1997). The TSST-C (as well as the adult version of the TSST) has been used extensively as a robust and reliable method for inducing social stress, and variants have been used in conjunction with animal interaction (e.g., Allen et al., 2002; Polheber & Matchock, 2013). The TSST-C was originally validated for use in 10-14 year olds (Buske-Kirschbaum et al., 1997), but the protocol used in this study is a specific adaptation validated for use in adolescents up to 17 years old (Stroud et al., 2009). The TSST-C involves a public speaking task and a mental arithmetic performance challenge. During the baseline rest period (20 minutes) rest period, participants will watch a science documentary (with no animal content) on a digital tablet. Participants will then be told about the task (anticipation). Then participants will have a 5-minute preparation period, and then they will be asked to speak on an academic topic for 5 minutes (e.g., give a plot summary and interpretation of a book of their choice). They will then be asked to complete a serial subtraction mental arithmetic task for 5 minutes. Per the Stroud et al. (2009) protocol, the serial subtraction task will be adjusted for age (13-14 year olds will subtract by 11s, 15-17 year olds will subtract by 17s). If an error is made, participants will be instructed to restart from the beginning.

Finally, there will be a 30-minute recovery period where they will continue to watch the science documentary. Throughout the TSST-C, participants will be asked to self-report their anxiety levels at each of the 6 phases and will wear a watch-like wristband (Empatica E4) to continuously measure heart rate data.

Compensation for the screening process will be a \$10 gift card (duration approximately 10 minutes). Youth who meet the eligibility criteria and who participate in the experiment will be compensated with a \$75 gift card (duration of the study approximately 2 hours, not including travel time to Tufts University).

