## **PROTECTION OF HUMAN SUBJECTS**

### **1. Risks to Human Subjects**

#### **a) Human subjects involvement and characteristics**

As described in the research plan, we will recruit 75 youth ages 13-17 to participate in this study. Children will be involved in this study, given that the specific aims of the study pertain to animal-assisted interventions for adolescents with social anxiety. This age range was selected due to the importance of adolescence as a critical period for the development of social anxiety.

Participants will be recruited via stratified sampling defined by scores on the Social Anxiety for Adolescents scale (SAS-A; La Greca & Lopez, 1998). We aim to recruit 25 participants in each of three strata as defined by scores of >50 (high anxiety), 36-50 (mid anxiety), and <36 (low anxiety) as recommended by La Greca (1999). Exclusion criteria include self-reported fear of or allergy to dogs. There are no exclusion criteria based on sex or race/ethnicity.

Eligible participants will be randomized into one of three conditions: 1) control group (no contact with a therapy dog); 2) social interaction with a therapy dog (no physical contact); and 3) social + physical interaction with a therapy dog. Participants in all three conditions will complete the validated Trier Social Stress Task for Children (TSST-C), which involves a public speaking task and a mental arithmetic performance challenge. During the experiment, participants will wear a clinical grade wearable sensor (similar to a watch). They will be asked to complete a self-report questionnaire of their anxiety level at baseline (State-Trait Anxiety Inventory – State scale; STAI), during each portion of the TSST-C, and at the end of the experiment. All sessions will be video recorded.

Each potential participant will be given a \$10 gift card to complete the screening process (approximately 15 minutes, can be completed at home via digital screening tool). Youth who meet the eligibility criteria will be invited to participate in the full experiment (approximately 2 hours), and will be compensated with a \$75 gift card as an incentive for participating in the study and for travel expenses (\$50 for participation, \$25 for travel costs). This compensation rate is necessary given the specific nature of our target sample and the time investment on the part of the participants, including travel to Tufts University.

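### The two dog conditions differ in social prompt as well as touch, so if the script follows the protocol's wording, a difference between them cannot be attributed to touch alone

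*Protocol*

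**What the plan says.** The Protocol's Background names two candidate mechanisms for Aim 1. The first is social interaction with an animal. For the other it says: "The second mechanism we will test is whether physically touching an animal buffers anxiety above and beyond social support alone".

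Participants and Procedure sets up three arms of 25: a stuffed toy dog (condition 1, control), a real dog with social interaction only (condition 2), and a real dog with social and physical interaction (condition 3). The section on human subjects involvement and characteristics gives the two dog arms as "2) social interaction with a therapy dog (no physical contact); and 3) social + physical interaction with a therapy dog". A touch-only arm is left out because "it would be impractical to block the possibility for social interaction while allowing physical interaction".

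The instructions to the two dog arms are then described. In condition 2, "participants will be told that the dog will be present, and they can socially interact with it at any point during the experiment"; talking and social referencing are the examples given, and touching is ruled out. In condition 3, participants hear that "the dog will be next to them and that they will be encouraged to interact socially and touch the dog".

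Other features are common to both dog arms. In each, "one therapy dog and his or her handler will accompany the participant during all phases of the TSST-C"; handlers are "trained to provide consistently minimal verbal contact, to reduce the confounding effects of handler variability"; and the dog is on a 6-foot leash. Sessions are filmed so that social referencing can be coded, and the video is kept for five years (Video Data; Data Safety and Monitoring Plan). The SAP's Analyses section models the STAI and physiological outcomes on condition, social anxiety, time point and the baseline value.

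**The concern.** The arm labels imply that condition 3 is condition 2 with touch added. The described instructions do not quite deliver that. Condition 2 is permitted to interact socially; condition 3 is urged to do so, and urged to touch as well.

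This matters because social interaction is the rival mechanism. Aim 1 is meant to separate what the dog does as a social presence from what touching it adds. If the arm with touch also receives the stronger social prompt, any advantage of condition 3 could come from touch, from more social engagement with the dog, or from both. The touch conclusion would then claim more than the design can show.

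**Working it through.** No figure in the plan measures this point, so the check is a comparison of text, followed by a count of what it affects.

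**1. The two instructions side by side** (Protocol, Participants and Procedure)

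| Feature | Condition 2 | Condition 3 | Intended difference? |
|---|---|---|---|
| Touch | not permitted | encouraged | yes |
| Social interaction | permitted (*can*), at any point | encouraged | no |
| Stated position of dog | *present* | *next to them* | not stated |
| Dog and handler in all phases | yes | yes | same |
| Handler speech | minimal | minimal | same |
| Leash | 6 feet | 6 feet | same |

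In the condition 3 sentence, *encouraged* governs both verbs: interacting socially and touching. The shared features in the last three rows do not set the strength of the social prompt, and no other section says that the prompts are matched.

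**2. Which contrast carries the touch question.** Three arms give three pairwise contrasts.
- 2 vs 1: a real dog with social interaction against the toy. It contains no touching of a dog.
- 3 vs 1: a real dog with social interaction and touch against the toy. It cannot separate touch from the dog's social presence.
- 3 vs 2: both arms have a real dog and only one allows touch. This is the only pairwise contrast that can address touch beyond social support.

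**3. Scope.** One of three contrasts and one of two Aim 1 mechanisms. Participants in that contrast: 25 + 25 = 50 of 75.

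**4. Whether the sample size section helps.** It does not. Its figures reproduce with a two-sample t test, taking alpha 0.05 as two-sided (the SAP does not state sidedness) and noncentrality = difference / (SD × √(2/n)).
- Heart rate: 12 / (12 × √(2/23)) = 3.39 on 44 df, power 0.912 against the stated 90%.
- STAI: 10 / (10.5 × √(2/25)) = 3.37 on 48 df, power 0.910 against the stated 90%.

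These concern the chance of detecting a difference between two groups. They say nothing about which component of condition 3 produced it.

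**The case against.** The strongest reply is that this rests on one verb in a description of the instructions. The actual script is not reproduced, and it may have used matched wording. Condition 2's licence is also explicit and, in one respect, more specific than condition 3's: "they can socially interact with it at any point during the experiment (i.e., talking, social referencing". One could read *encouraged* as aimed mainly at touch. This stands in part, and it is why the point is conditional on the script. But permission is still not encouragement, the grammar covers both verbs, and the described instructions are what the plan commits to.

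A second reply is that closeness and some social engagement come with touching a dog, and that the Protocol openly accepts that touch cannot be had without social interaction. That is right, and it disposes of most of the difference in stated position. It does not cover the social prompt, because telling one arm that it may interact and the other that it should is not inherent in touch.

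A reader might go further and infer that the dog was kept farther away in condition 2. The documents do not support that: a dog described as present may also be beside the participant, and no section gives a distance. Nor does the absence of touch from the named video codes show that touch will go unrecorded.

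**Conclusion.** The point holds, conditionally. If the script follows the Protocol's wording, 3 vs 2 varies the social prompt as well as touch, and a difference cannot be attributed to touch alone. The stated dog position is a secondary matter.

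The size and direction of any bias cannot be derived from the documents, and none is claimed. A reader might infer that the 3 vs 2 result is invalid or that the trial's dog effects are compromised. Neither follows. Participants are randomised, so 3 vs 2 remains a valid comparison of two packages, and both dog-versus-control contrasts are unaffected as package comparisons. What is at risk is the interpretation of one contrast, which carries one of the two Aim 1 mechanisms. It should be corrected because the correction is nearly free and bears directly on the question the trial set itself.

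**What to change.** **If sessions remain:** use identical social-interaction wording in conditions 2 and 3, so that only the touch instruction differs, and state the dog's position in each arm, accepting that some closeness belongs to touch. The cost is a change of wording in the participant script and one line on position.

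**If sessions are complete** (the SAP's Analyses section is in the past tense): report the script actually used. If it followed the Protocol, describe 3 vs 2 as the effect of the social + physical package, not of touch alone. The cost is a change in how the contrast is described.

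**Optional, if the videos are still within the five-year retention:** report coded social referencing and touch by arm. This would be a descriptive check beside the as-randomised comparison and not an adjustment to it, since both behaviours arise after randomisation. Footage for the 50 dog-arm sessions is 50 × (5 + 5 + 5) = 750 minutes, or 12.5 hours, for preparation, speech and mental math. Adding the 20-minute baseline and 30-minute recovery gives 50 × 65 = 3,250 minutes, about 54 hours. Anticipation has no stated length and is not counted. These are footage times only; coder training and any double coding would add to them.

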## Measures

To test the mechanism of action for canine interaction in reducing social anxiety in adolescents, we will collect three levels of outcome data: a) self-reported experience (anxiety), b) autonomic physiological reactivity (heart rate), and c) cognitive performance (error rates on mental math task).

*Social anxiety.* The SAS-A will be used to assess overall level of social anxiety. The SAS-A was designed for use in adolescence and has been validated extensively across many samples and in multiple languages (e.g., Garcia-Lopez et al., 2011; La Greca & Lopez, 1998). The SAS-A contains 18 items that include three domains of social anxiety: fear of negative evaluation from peers, social avoidance and distress in new situations, and generalized social avoidance.

*Self-Report Experience:* Self-reported affective experience will be measured using the state scale of the State-Trait Anxiety Inventory (STAI; Spielberger et al., 1983), which is validated for use in adolescence and is commonly used with the TSST. The STAI state scale contains 20-items rated on a four-point scale, and has consistently demonstrated excellent reliability (ranging from  $\alpha = .86$  to  $.95$ ; Spielberger et al., 1983) and construct validity (Spielberger, 1989). Anxiety will be measured at six time points, during: (1) baseline, (2) anticipation (3) preparation, (4) speech, (5) mental math, and (6) recovery.

*Autonomic physiological reactivity:* Heart rate and electrodermal activity will be collected continuously using a clinical grade wristband sensor (Empatica E4; Garbarino et al., 2015).

*Cognitive Performance:* Cognitive performance during the social stressor task will be measured to understand how anxiety and AAI influence cognitive function. As recommended by existing research with the TSST paradigm (e.g., Simeon et al., 2007), we will measure cognitive performance during the mental arithmetic task by tracking the number of errors and lowest number reached by participants on the mental math task. Better performance will be characterized by fewer errors and reaching a lower number during serial subtraction.

*Demographic Characteristics:* In addition to the measures assessing the primary aims, we will also collect demographic covariate information from participants on age, sex, race/ethnicity, and current pet ownership.

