## *3. Performance Data*

Performance during the mental arithmetic portion of the TSST-C (number of errors and lowest number reached) will be recorded securely in REDCap.

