### *Analyses:*

To test our confirmatory hypotheses, we conducted two three-way analyses of variance (ANOVA) with either self-reported anxiety (STAI), autonomic reactivity (electrodermal activity [EDA] and heart rate [HR]) as the dependent variable. For these outcomes, there were two between-subjects factors, condition (social, social + physical, control) and social anxiety (SA; centered continuous predictor), and one within-subjects factor, time point (1, 2, 3, 4, 5, 6). We included baseline STAI, EDA, or HR at time point 1 as a centered continuous covariate. For cognitive performance, we conducted ANOVAs that treated condition as a between-subjects categorical factor and social anxiety as a centered continuous predictor.

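### The subtraction step depends on age (11s or 17s), yet no step conversion or task-version term is described for the lowest number reached: a minor, nearly free precision gain

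*Protocol*

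**What the plan says.** The Protocol's description of the TSST-C (Participants and Procedure) sets the subtraction step by age: "13-14 year olds will subtract by 11s, 15-17 year olds will subtract by 17s". It adds a restart rule: "If an error is made, participants will be instructed to restart from the beginning".

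Under Measures, one scoring direction serves both versions: "Better performance will be characterized by fewer errors and reaching a lower number during serial subtraction". The Performance Data section lists what is stored as "number of errors and lowest number reached". Neither place describes dividing by the step size or standardising within version.

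The SAP (Analyses) models these scores as follows: "For cognitive performance, we conducted ANOVAs that treated condition as a between-subjects categorical factor and social anxiety as a centered continuous predictor". No age or version term appears. Age is nevertheless available, because Measures includes "demographic covariate information from participants on age, sex, race/ethnicity, and current pet ownership".

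The screener is used to assess "pre-existing level of social anxiety to inform stratified randomization". No section describes balancing age band or task version across arms.

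**The concern.** From a common starting number, a run of k correct subtractions lowers the number by 11k in the younger version and 17k in the older. Two participants who perform equally well in steps then receive different scores. The design itself creates this source of variation, and the model has no term to absorb it.

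Two consequences are possible for this score. The version difference can sit in the residual and reduce power for the condition contrast. It can also mix with the social-anxiety main effect, because social anxiety is not randomised. That effect is not a numbered aim, but the Protocol shows interest in it: "Cognitive performance during the social stressor task will be measured to understand how anxiety and AAI influence cognitive function".

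**Working it through.** **The plan's own figure.** The SAP gives no power or sample size for the cognitive scores. Its heart-rate figure reproduces (difference 12, SD 12, two-sided 0.05, 90% power: t-test solution 22.02, rounded up to 23 per group), but nothing below depends on it.

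**Inputs.** From the documents: steps of 11 and 17, 25 per arm, alpha 0.05. Assumed, because the documents give no values: a common starting number; younger mean k = 12 correct steps; SD s = 5 steps in both bands; share aged 13-14 p = 0.4; older/younger step ratio r; a condition effect of 4 steps (4/5 = 0.8 SD).

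**Version share of score variance.**
- Gap between version means: g = 17rk − 11k.
- Between-version variance: B = p(1−p)g².
- Within-version variance: W = p(11s)² + (1−p)(17s)².
- Share = B/(B+W).

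At r = 1: g = 204 − 132 = 72; B = 0.24 × 5184 = 1244; W = 0.4 × 3025 + 0.6 × 7225 = 5545; share = 1244/6789 = 18.3%.

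**Power by simulation** (8000 runs per row; one arm against control; condition × social-anxiety model, without and with a version factor; no difference in SAS-A between age bands):

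| r | Version share | Power as planned | Power with version |
|---|---|---|---|
| 1.0 | 18.3% | 65.9% | 76.0% |
| 0.9 | 10.3% | 70.7% | 76.4% |
| 0.8 | 4.0% | 74.3% | 76.4% |
| 0.7 | 0.5% | 76.5% | 76.5% |
| 11/17 | 0% | 77.0% | 76.3% |
| 0.5 | 3.7% | 76.4% | 76.5% |

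At r = 11/17 the two versions have the same mean drop (17 × 11/17 = 11 per younger step), so there is nothing to recover and the factor costs 77.0 − 76.3 = 0.7 points.

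**Sensitivity at r = 1.**
- *Mean steps.* k = 8: 71.9% against 76.3%, a gain of 4.4 points. k = 15: 60.9% against 75.9%, a gain of 15.0 points.
- *SD of steps, k = 12.* Share 26% at s = 4, 9.8% at s = 7.2 and 6.5% at s = 9. With the effect held at 0.8 SD, power is 70% against 76% at s = 7.2 and 71% against 74% at s = 9 (4000 runs). The share depends on k and s only through k/s, so k = 12 with s = 4 matches k = 15 with s = 5 (both ratios 3). At the same 0.8 SD effect the gain is again about 15 points.
- *Age mix.* Over k = 8 to 15 and p = 0.3 to 0.5 (s = 5), the share runs from 7.5% to 28.3%.
- *Starting number, k = 12, s = 5.* A start 36 higher for the older band halves the gap to 36. The share falls to 5%, and power is 74% against 77%. A start 72 higher removes the gap.

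**Social-anxiety main effect, no true effect, nominal 5%.** False positives in the planned model if mean SAS-A differs by 0.3 / 0.6 SD between age bands:
- r = 1: 7.8% / 16.4%
- r = 0.8: 5.4% / 7.2%
- r = 11/17: 5.1% / 4.7%

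With the version factor the rate is 4.7% to 5.2% throughout.

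**Condition-by-social-anxiety interaction, no true effect.** The 2-df F test rejects in 4.5% to 5.3% of runs.

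**Rescoring alone.** Dividing by 11 or 17 does not replace the factor. At r = 11/17 the older mean is 12 × 11/17 = 7.8 steps against 12, so rescoring creates a version gap that the original scale did not have. With a 0.6 SD shift in SAS-A, false positives for the social-anxiety main effect are then 13.8% without the factor and 5.1% with it.

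**The case against.** The case for leaving the plan alone is substantial.

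- **Unknown inputs.** The Protocol takes the age adjustment from a cited procedure that may set the starting numbers, and nothing is said about step counts. Where older participants make 0.8 times as many steps or fewer, the gain is about 2 points at most (at k = 12, s = 5). The restart rule makes the lowest number reflect the longest correct run, which could be widely spread, and a larger SD shrinks the effect. This stands: no single figure can be claimed.
- **Scoring scale.** A reader might infer that the number is certainly analysed raw. The documents give a direction and a stored quantity, not an analysis scale. The supportable statement is that no conversion is described.
- **Peripheral measure.** The Protocol's Approach and the opening of Measures summarise cognitive performance as error rates. The lowest number is an additional score, and the SAP sizes the trial on heart rate and STAI. This also stands.
- **Validity.** Omitting a prognostic covariate from a randomised comparison is legitimate. A reader might infer that Aim 1 is biased or that the Aim 2 moderation test is invalid. Neither is supported: randomisation makes version independent of condition in expectation, and the interaction test kept its error rate.

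What remains is a difference in scale that the design creates and a model without the term that would absorb it. Collecting age keeps the adjustment possible, but the SAP does not commit to it.

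**Conclusion.** The point holds as a minor free improvement, limited to the precision and interpretability of the lowest-number score. The possible gain runs from none (step ratio near 11/17, or a suitably higher start for the older band) to about 15 points of power (equal steps with a high mean or a small SD). These figures are illustrations resting on assumed step counts, SD, starting number and age mix.

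The social-anxiety main effect on this score is confounded with version only if two things are true together: SAS-A differs between the age bands, and the mean score differs between versions. The documents say neither, so it would be wrong to read the 8% and 16% false-positive rates as established. A version effect on the error count through difficulty is conceivable but has not been quantified.

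**What to change.** Add task version (13-14 against 15-17, derived from the age already collected) as a factor in the ANOVA of lowest number reached. For consistency, add it to the error-count ANOVA as well, acknowledging that no benefit has been shown there.

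If the score is re-expressed as steps, (starting number − lowest number)/11 or /17, do so only together with that factor, and state the starting number.

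The cost is one degree of freedom per model and no new data or change of procedure. The SAP's Analyses section is written in the past tense. If these ANOVAs have already been run, report the version-adjusted models beside them rather than in their place.
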